1 PROTOCOL SUMMARY

1.1 Synopsis

Background and Rationale:

This study will investigate the efficacy of two experimental 5% potassium nitrate (KNO₃) dentifrices, one containing alumina and sodium tripolyphosphate (STP), the other alumina, STP and high cleaning silica, to reduce extrinsic dental stain and thereby whiten the teeth, compared to a marketed regular fluoride dentifrice with 8 weeks twice daily brushing.

Objectives and Endpoints:

Objectives	Endpoints
Primary	
To evaluate the change in extrinsic dental stain after 8 weeks twice daily use of a '5% KNO ₃ /1% alumina/5% STP' dentifrice, a '5% KNO ₃ /1% alumina/ 5% STP/2% silica' dentifrice and a regular fluoride dentifrice, as measured by Total Modified Lobene Stain Index (Total MLSI (Area x Intensity)).	Change from baseline in mean Total MLSI (Area x Intensity) score at week 8.
Secondary	
To evaluate the change in extrinsic dental stain after 4 weeks twice daily use of a '5% KNO ₃ /1% alumina/5% STP' dentifrice, a '5% KNO ₃ /1% alumina/ 5% STP/2% silica' dentifrice and a regular fluoride dentifrice, as measured by Total Modified Lobene Stain Index (Total MLSI (Area x Intensity)).	Change from baseline in mean Total MLSI (Area x Intensity) score at week 4.
To compare the change in extrinsic dental stain after 4 & 8 weeks twice daily use of either a '5% KNO ₃ /1% alumina/5% STP' dentifrice or a '5% KNO ₃ /1% alumina/ 5% STP/2% silica' dentifrice, compared to a regular fluoride dentifrice, as measured by Total MLSI (Area x Intensity).	Change from baseline in mean Total MLSI (Area x Intensity) score at weeks 4 & 8.
To evaluate and compare the change in tooth shade (color) after 4 and 8 weeks twice daily use of either a '5% KNO ₃ /1% alumina/5% STP' dentifrice or a '5% KNO ₃ /1% alumina/ 5% STP/2% silica' dentifrice, compared to a regular fluoride dentifrice, as measured by the VITA Bleachedguide 3D-MASTER.	Change from baseline in mean VITA shade score (examiner assessed) at weeks 4 & 8.
To evaluate and compare the changes in dental stain at specific tooth sites (along gingival margin, inter-proximally and on the body of the tooth) after 4 and 8 weeks twice daily use of either a '5% KNO ₃ /1% alumina/5% STP' dentifrice or a '5% KNO ₃ /1% alumina/ 5% STP/2% silica' dentifrice, compared to a regular fluoride dentifrice, as measured by Total MLSI (Area x Intensity).	Change from baseline in mean MLSI (Area x Intensity) in: 
 • Gingival sites • Interproximal sites • Body sites
To evaluate and compare change in extrinsic dental stain after 4 and 8 weeks twice daily use of either a '5% KNO ₃ /1% alumina/5% STP' dentifrice or a '5% KNO ₃ /1% alumina/ 5% STP/2% silica' dentifrice, compared to a regular fluoride dentifrice, as measured by MLSI (Area) and MLSI (Intensity).	Change from baseline in mean MLSI (Area) and MLSI (Intensity)
Exploratory	
To evaluate and compare the change in tooth color co-ordinates after 4 and 8 weeks twice daily use of either a '5% KNO ₃ /1% alumina/5% STP' dentifrice or a '5% KNO ₃ /1% alumina/ 5%	Change from baseline in mean tooth shade, L*, a*, b*, W _D and ΔE* determined using the VITA

STP/2% silica' dentifrice, compared to a regular fluoride dentifrice, as measured using the VITA EasyShade.	EasyShade instrument at weeks 4 & 8
Safety	
To assess the safety and tolerability of the two experimental KNO ₃ dentifrices.	Treatment emergent adverse events

Mean MLSI values calculated for the facial surfaces of the six maxillary anterior teeth and six mandibular anterior teeth, and the lingual surfaces of the six mandibular anterior teeth.

Mean tooth shade/color values are calculated for the facial surfaces of the 4 central and lateral maxillary incisors.

Study Design:

This will be a single-center, 8-week, randomized, controlled, single-blind (clinical examiner(s) and VITA EasyShade operator), three treatment-arm, parallel design, stratified clinical study in healthy volunteers with clinically confirmed dental stain (originating from the diet and/or smoking) on the surfaces of their anterior teeth.

Potential subjects will attend a screening visit (Visit 1, Day 0) to determine their suitability to participate. Having obtained their written informed consent, relevant details of their medical history and current medications will be recorded, followed by oral soft tissue (OST) and oral hard tissue (OHT) examinations. Subjects meeting the relevant study criteria, will be considered as eligible to proceed for baseline assessments on the same day.

At the baseline visit (Visit 2, Day 0), eligible subjects will undergo clinical and instrumental assessments of extrinsic dental stain (MLSI: facial surfaces of the six maxillary anterior teeth and six mandibular anterior teeth, and the lingual surfaces of the six mandibular anterior teeth) and tooth color (VITA Bleachedguide 3D-MASTER and VITA EasyShade instrument: facial surfaces of the central and lateral maxillary incisors).

Qualifying subjects will be stratified by baseline Total MLSI _(A x I) (calculated for the facial surfaces of the six maxillary anterior teeth and six mandibular anterior teeth only) and smoking status and randomized to one of the three study treatments. Randomized subjects will be instructed to brush twice daily (for 2 minutes, morning and evening) with their assigned study dentifrice for the next 8 weeks. Extrinsic dental stain and tooth color assessments will be repeated after 4- and 8-weeks treatment.

Study Products:

Experimental Dentifrices	Reference Dentifrice
5% KNO ₃ dentifrice with 1% alumina and 5% STP	5% KNO ₃ dentifrice with 1% alumina, 5% STP and 2% high cleaning silica
Each study dentifrice will contain 0.2542% sodium fluoride (1100 parts per million (ppm) fluoride)	

All dentifrices will be applied in the same manner and will be brushed on to the teeth, twice daily (morning and evening) for 2 timed minutes.

Type and Planned Number of Subjects:

Study subjects of either sex and any gender, aged of 18-65 years, will be in good general and oral health, with the level of extrinsic tooth stain and color required at baseline to participate in the study.

Sufficient subjects will be screened to randomize approximately 300 subjects to study treatment (approximately 100 per treatment group) to ensure approximately 270 evaluable subjects complete the study.

Statistical Analysis Summary:

For the analysis of the change from baseline in the mean Total MLSI (Area x Intensity) and the change from baseline in the mean VITA shade score, separate Mixed Models with Repeated Measures will be used. Fixed effects will be included for smoking status, study product, visit and study product x visit interaction. The respective baseline score will be included as a covariate. Subject will be included as a repeated measure with unstructured covariance matrix. Kenward Rogers degrees of freedom approach will be applied. The least square means for each Experimental Dentifrice at week 8 will be presented based on observed margins and used to test for a negative change from baseline. The differences between least square means for each Experimental Dentifrice compared to the Reference Dentifrice at week 8 will be presented and used to test for a difference between products.

The hypothesis testing of the of change from baseline in the mean Total MLSI (Area x Intensity) and the change from baseline in the mean VITA shade score will employ a graphical approach methodology, as per Bretz *et al* ([Bretz et al., 2009](#)) in order to maintain an overall two-sided familywise error rate of 5% within each Experimental Dentifrice (10% overall). The adjusted two-sided p-values and simultaneous 95% confidence intervals (following graphical testing approach) will be provided for all comparisons.

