4 STUDY DESIGN

4.1 Overall Design

This will be a single-center, 8-week, randomized, controlled, single-blind (clinical examiner(s) and VITA EasyShade operator), three treatment-arm, parallel design, stratified clinical study in healthy volunteers with a propensity to form dental stain. It has been designed to investigate changes in tooth stain and color, following twice-daily use of two experimental dentifrices, after four- and eight-weeks twice daily use; a regular fluoride dentifrice will be included as reference dentifrice. Sufficient subjects will be screened to randomize approximately 300 subjects to study treatment to ensure approximately 270 subjects complete the study.

At screening (Visit 1, Day 0), subjects will give their written informed consent to participate in the study. Demography, relevant medical history and current medications/treatments will be recorded, followed by OST and OHT examinations. Subjects meeting the relevant study criteria, will be considered eligible to proceed for baseline assessments on the same day..

At baseline (Visit 2, Day 0) subjects, having refrained from oral hygiene procedures for at least 6 hours, will undergo clinical assessment of the stain on the facial surfaces of their six maxillary anterior teeth and six mandibular anterior teeth (tooth numbers 6-11 and 22-27) and the lingual surfaces of their six mandibular anterior teeth (tooth numbers 22-27) using the MacPherson modification ([Macpherson et al., 2000](#)) of the Lobene Stain Index ([Lobene, 1968](#)) (MLSI). The shade (color) of the facial surfaces of the central and lateral maxillary incisors (tooth numbers 7-10) will then be assessed clinically using the VITA Bleachedguide 3D-MASTER ([Gómez-Polo et al., 2015](#)) and the color of the same surfaces will be evaluated using the VITA

EasyShade instrument ([Tung et al., 2002](#)). Subjects who fulfil all inclusion/exclusion criteria will be enrolled into the study.

Qualifying subjects with a Total MLSI $(A \times I) \geq 15$ for the facial surfaces of the 12 anterior teeth and a mean tooth shade ≥ 11 on the facial surfaces of the 4 maxillary incisors, who meet all other entry criteria, will be stratified according to their baseline Total MLSI $(A \times I)$ (low < 45 ; high ≥ 45) and smoking status (smoker; non-smoker) and randomized to study treatment.

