The experimental dentifrices, when marketed, will be indicated for DH. It is anticipated they will be purchased by consumers with DH who desire whiter teeth (less dental stain). However, the study objectives relate solely to dental stain and tooth color, both of which are independent of DH; thus, study subjects are not specifically required to experience DH nor do the exclusion criteria exclude subjects with DH. Subjects will be stratified according to their baseline tooth stain score and smoking status to ensure balance across the three treatment groups.

An 8-week treatment period is deemed sufficient to observe the anticipated clinical benefits; 4-week assessments are included should more rapid clinical effects occur.

The clinical measures used in this study, MLSI and VITA shade guide, are well established in the scientific literature for the evaluation of dental stain and tooth color respectively ([Joiner and Luo, 2017](#)). VITA shade guides are routinely used by dentists in practice to assess the color of natural teeth to enable accurate matching of prosthetic devices (e.g. crowns, partial dentures) to the natural dentition. The VITA shade guide selected for use in this study (VITA Bleachedguide 3D-MASTER) has the advantage over the classic VITA shade guide in providing a linear presentation of tooth shade which will enable more accurate assessment of shade changes ([Paravina, 2008](#)). Furthermore, it is accepted by the American Dental Association for use in determining the efficacy of tooth whitening products ([ADA, 2020](#)).

The VITA EasyShade instrument, whilst being a more recent approach to the assessment of tooth color, has been shown to provide precise measurement of tooth color in a previous clinical study ([Dožić et al., 2007](#)) and offers the potential for objective, examiner-independent evaluation of tooth color ([Knezovic Zlataric et al., 2016](#)). It is included in this study is to provide further information on tooth color-specific variables (e.g. L^* , a^* , b^* , WID and ΔE) that could provide greater understanding on the tooth-cleaning properties of the experimental dentifrices.

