12 STATISTICAL CONSIDERATIONS AND DATA ANALYSES

12.1 Sample Size Determination

The study will be powered sufficiently (>90%) to provide evidence of superiority for an Experimental Dentifrice compared to the Reference Dentifrice for both stain removal and whitening after 8 weeks under the graphical approach method (with initial two-sided alpha

allocation of 5% for testing within each Experimental Dentifrice) to adjust for multiple comparisons and preserve a two-sided 10% family wise error rate as described in section 12.3.

Table 12-1 Sample Size Power by Endpoint at 5% and 2.5% Significance Levels with 90 Subjects per Arm

Endpoint at Week 8	Assumptions		Independent power from 90 subjects per arm for each endpoint by two-sided significance level ³		Power from graphical approach to achieve statistical significance at 5% level ⁴
	Mean Difference	Standard Deviation (SD)	5%	2.5%	
Within Experimental Dentifrice change from baseline in mean Total MLSI (Area x Intensity) ¹	0.6	0.4	>99.9%	>99.9%	>99.9%
Comparison with Reference Dentifrice in change from baseline in mean Total MLSI (Area x Intensity) ¹	0.3	0.4	99.8%	99.7%	99.8%
Within change from baseline in the mean VITA shade score ²	2	2	>99.9%	>99.9%	>99.9%
Comparison with Reference Dentifrice in change from baseline in the mean VITA shade score ²	1	2	91.5%	86.1%	90.2%

1) Estimates of mean difference and SD were based on results from previous GSKCH studies of similar design

CCI [REDACTED]

2) Estimates of mean difference and SD were based on results from a previous GSKCH study of similar design

CCI [REDACTED] Within treatment study reductions in the mean VITA shade score are expected to be greater in this study due to greater baseline VITA shade scores and an 8 week primary assessment instead of 4 weeks. As such, the SD is also assumed to increase, so an effect size (mean difference/SD) of 0.5 is assumed.

3) Based on carrying out a two tailed one-sample (within Experimental Dentifrice) or two-sample (Comparison with Reference Dentifrice) t-test at the 5% significance level using PASS software version 19.0.1.

4) Simulation using SAS 9.4 software based on stated assumptions for all endpoints and graphical approach analysis detailed in section 12.3.

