As detailed in the independent sample size calculations in Table 12-1, the minimum required sample size assessment depends almost entirely on the mean VITA shade score reduction comparison between Experimental and Reference Dentifrices. Simulation shows that under the graphical approach methodology (Section 12.3) and the above underlying assumptions for an Experimental Dentifrice, the power to show statistical significance in all 4 comparisons for that Experimental Dentifrice (reduction from baseline and superior reduction compared to Reference Dentifrice in both mean Total MLSI [Area x Intensity] and mean VITA shade score) is > 90%.

Approximately 100 subjects per group (approximately 300 in total) will be randomized to account for a drop-out rate of up to 10% prior to Week 8.

Property of GSK Consumer Healthcare - Confidential

May not be used, divulged, published or otherwise disclosed without the consent of GSKCH

CCI [REDACTED]

Clinical Protocol Template v9.0

Page 51 of 63

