4.4.2.1.1 Statistical Hypothesis, Model and Method of Analysis

The following null and alternative hypotheses will be evaluated:

- H_0 : There is no difference between baseline and week 8
- H_1 : There is a difference between baseline and week 8

The following study product comparisons will be analyzed:

- For Experimental Dentifrice 1, baseline versus week 8
- For Experimental Dentifrice 2, baseline versus week 8

The change from baseline in the mean VITA shade score will be analysed using a MMRM. Fixed effects will be included for smoking status, baseline Total MLSI (AxI) stratification (< 45 or ≥ 45), study product, visit and study product x visit interaction. The baseline mean VITA shade score will be included as a covariate. Subject will be included as a repeated measure with unstructured covariance matrix. Kenward Rogers degrees of freedom approach will be applied. The least square means for each study product at week 8 will be presented based on observed margins and used to test for a non-zero change from baseline. If unstructured covariance matrix does not converge, compound symmetry covariance matrix will be used.

Using the above model, the adjusted mean change from baseline in the mean VITA shade score will be reported by study product group along with 95% CIs and p-values testing for a non-zero change from baseline will be provided in Table 14.2.3.2.1. For each Experimental Dentifrice, only adjusted p-values following the graphical approach (see [Figure 4-1](#)) will be presented. Significance testing will be conducted at the two-sided 5% significance level.

The assumption of normality and homogeneity of variance in the MMRM will be investigated. In case of violation of these assumptions, a suitable nonparametric test (the Van Elteren test, adjusted for the randomization stratification) will be performed for each comparison at week 8 and results will be provided to support the MMRM results.

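### The VITA shade model leaves out the pre-randomization EasyShade reading of the same four teeth, a small precision gain available at almost no cost

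*Protocol*

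**What the plan says.** - **Model.** Protocol 1.1 (Statistical Analysis Summary) and 12.3.1 fit an MMRM to change in mean VITA shade score, with smoking status, product, visit and product-by-visit as fixed effects. On baseline: "The respective baseline score will be included as a covariate". SAP 4.4.2.1.1 adds the baseline Total MLSI stratum and states: "The baseline mean VITA shade score will be included as a covariate". SAP 4.4.2.3.1 takes the comparison with Reference from the same model.
- **Unused reading.** At Visit 2, after the examiner's shade score, "the color of the same surfaces will be evaluated using the VITA" EasyShade (Protocol 4.1). Protocol 8.2.1 makes this step 3 and randomization step 6. Protocol 9.2.3 confirms teeth 7-10 and records both a Bleachedguide shade and L*, a*, b*. SAP 4.4.3.1 and 4.4.3.1.1 use these data only as exploratory outcomes and as baselines for those outcomes.
- **Instrument.** Protocol 4.2 says that it "offers the potential for objective, examiner-independent evaluation of tooth color".
- **Role of the comparison.** Protocol 12.1 says that "the minimum required sample size assessment depends almost entirely on the mean VITA shade score reduction comparison" between Experimental and Reference. Table 12-1 gives that comparison 91.5% power at 5%, 86.1% at 2.5% and 90.2% under the graphical procedure, against a target above 90%.

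**The concern.** The examiner's baseline score is one unreplicated assessment, averaged over up to four teeth, with each determination made in 5-7 seconds (Protocol 9.2.2). It is also the entry filter, at 11 or more (Protocol 5.2). If it carries measurement error, it adjusts imperfectly for true baseline shade. A second pre-randomization measure of color on the same teeth could recover part of what is missed.

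The comparison concerned is the one that sets the sample size, and its 90.2% power under the graph is close to the 90% target. A smaller residual variance would narrow its confidence interval with no extra subjects or procedures.

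**Working it through.** **1. Reproduce the stated power.** Inputs from Protocol 12.1: difference 1 and SD 2 ("so an effect size (mean difference/SD) of 0.5 is assumed"), 90 per arm, two-sided 5% ("allocation of 5% for testing within each Experimental Dentifrice"). Method: "Based on carrying out a two tailed one-sample (within Experimental Dentifrice) or two-sample (Comparison with Reference Dentifrice) t-test".

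Noncentrality = 1 / (2 × √(2/90)) = 3.354, with 178 df. Power is 91.6% at 5% and 86.2% at 2.5%, against the stated 91.5% and 86.1%, so the figures reproduce. The 90.2% cannot be re-run without the alpha graph, but it lies between the two. No covariate enters this calculation.

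**2. Assumptions.** The documents give no reliability for the examiner's score and no correlation between EasyShade and visual shade. I assume:
- reliability of the visual mean, *rel*: 0.7-0.9 (middle 0.8);
- correlation of true shade, baseline to week 8, *rT*: 0.8-0.95 (middle 0.9);
- correlation of EasyShade with true shade, *c*: 0.6-0.9 (middle 0.8);
- examiner errors independent across visits, and independent of EasyShade error.

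**3. Fall in residual variance, middle case.**
- Week-8 VITA with baseline VITA: r1 = rT × rel = 0.9 × 0.8 = 0.72, so R² = 0.518.
- Week-8 VITA with EasyShade: r2 = c × rT × √rel = 0.8 × 0.9 × 0.894 = 0.644.
- Between the two baselines: r12 = c × √rel = 0.716.
- R² with both = (r1² + r2² − 2·r1·r2·r12) / (1 − r12²) = (0.518 + 0.415 − 0.664) / 0.488 = 0.552.
- Variance ratio = (1 − 0.552) / (1 − 0.518) = 0.929, a fall of about 7%. This is worth 90 / 0.929 ≈ 97, or about 7 more subjects per arm.

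Across the ranges the fall runs from 0.6% (*rel* 0.9, *rT* 0.8, *c* 0.6) to 19% (*rel* 0.7, *rT* 0.95, *c* 0.9).

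**4. Power at two-sided 5%, 90 per arm.** The result depends on what SD 2 stands for. If it is the SD of change, and variances are equal at baseline and week 8, then adjusting for baseline VITA alone multiplies the variance by (1 + r1)/2 = 0.86. The residual SD is then 2 × √0.86 = 1.855.

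| Reading of SD 2 | Planned model | With EasyShade |
|---|---|---|
| Residual SD | SD 2.000, 91.6% | SD 1.928, 93.3% |
| SD of change | SD 1.855, 94.9% | SD 1.788, 96.2% |

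Over the full ranges, power with EasyShade is 91.7% to 96.0% on the first reading. On the second, the planned model alone already gives 93.4% to 96.5%.

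**5. If the examiner's error persists.** Suppose half of the examiner's error variance for a subject is the same at both visits. In the middle case r1 becomes 0.72 + 0.5 × 0.2 = 0.82, while r2 and r12 are unchanged. The fall in residual variance drops to about 2%, and power on the first reading is 92.1%.

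**The case against.** The strongest reply is that nothing is wrong. Adjusting a change score for its own baseline is standard, and relative to a power calculation with no covariate the plan already gains precision. That stands.

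A reader might go further and infer any of the following, none of which the documents support:
- **The study is short of power.** Table 12-1 applies SD 2 to change from baseline in an unadjusted t-test, so it most naturally reads as the SD of change. On that reading the planned model is already at about 94.9% in the middle case.
- **The model adjusts for nothing but the baseline score.** It also has smoking status and, in the SAP, the MLSI stratum. The statement holds only for baseline color.
- **The examiner's score is known to be unreliable.** No figure is given; a weighted kappa is only planned (Protocol 12.3.4, SAP 4.6). EasyShade too is one reading per tooth.
- **EasyShade error is independent of the examiner.** Protocol 4.2 claims only a potential for this. Protocol 9.2.3 has the clinical examiner take the reading, and only from the middle of each tooth.

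Two technical objections also stand. One examiner scores every visit, so a stable offset for a subject is already captured by baseline VITA. The entry cut-off narrows the range of true shade as well, which weakens EasyShade as a predictor too. Finally, VITA shade is a secondary endpoint, and study success (Protocol Section 3) rests on within-product MLSI, which this change does not touch.

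None of this makes the covariate harmful. It limits how much can be claimed for it.

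**Conclusion.** The point holds as a cheap improvement. A pre-randomization measure of color on the same four teeth is collected and left out of the model for the comparison that drives the sample size. Including it should reduce residual variance, but the amount is unknown. Under the assumed correlations it is 0.6% to 19%, with about 7% in the middle case. That is worth 1.7 points of power (91.6% to 93.3%) if SD 2 is residual, or about 1.3 points (94.9% to 96.2%) if it is the SD of change. Persistent examiner error or a weak link between instrument and visual shade would bring the gain close to zero. The planned analysis is valid without it.

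**What to change.** Before unblinding, amend SAP 4.4.2.1.1 to add one baseline EasyShade measure, averaged over teeth 7-10, as a second continuous covariate. The comparison with Reference (4.4.2.3.1) and the week-4 results (4.4.2.5.1) then follow by reference.

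- **Choose one measure in advance.** WI_D is already derived in SAP 4.4.3.1. The instrument's Bleachedguide shade (Protocol 9.2.3) is on the endpoint's own scale, but SAP 4.4.3.1 gives no derivation for it.
- **Missing baseline EasyShade.** Substitute the overall baseline mean so that no subject is dropped. SAP 4.4.4 rules out imputation, so state there that this covariate is an exception.
- **Limit the scope.** SAP 4.4.3.1.1 borrows the 4.4.2.1.1 model for the EasyShade outcomes. Say that the new term applies to the VITA shade score only.
- **Record the change in SAP Section 5,** which already documents the added MLSI stratum term.

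The cost is a few lines of SAP text and one degree of freedom among about 270 evaluable subjects, with no new data. The downside is little gain if the instrument tracks visual shade poorly.
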